In 2023, a cluster randomized non-inferiority trial was completed in Kampong Thom province Cambodia (n=1546) to assess pregnant women's adherence to MMS compared to IFA supplementation during pregnancy (Hoang et al, 2024). In-depth interviews were completed with study participants who were high adherers (>80%), low adherers (<80%), and those who did not complete the trial. Thematic analysis revealed a range of factors influencing adherence. At the individual level, forgetfulness and negative pregnancy-related experiences (e.g., nausea, fatigue) emerged as barriers for low adherence. Conversely, high adherers highlighted establishing routines, using visual cues (cue to action) in the house as a stimulus or trigger to take the prenatal, and positive beliefs in MMS benefits as facilitators.

Interpersonal factors significantly influenced adherence. Strong existing norms around IFA and discouragement from family/friends during pregnancy-related symptoms were barriers for some. On the other hand, support from family (husbands, mothers-in-law) and healthcare providers, including reminders and endorsement of MMS, were enablers for high adherence. No institutional barriers were identified. However, institutional enablers included endorsement by government health providers and counseling from healthcare professionals. In conclusion, it was found that factors that influenced adherence to MMS included pregnant women's knowledge about the importance of supplementation during pregnancy, the use of visual cues in the house, the strength of ANC counseling, and family and community influence. Based on these findings, strategies must involve pregnant women, family members, and midwives to effectively scale up and promote MMS adherence.

The Trial of Improved Practices Study (TIPS) is a participatory formative research technique used to test and refine potential health interventions, focusing on behavior change on a small scale before introducing them on a large scale (The Manoff Group, 2005). TIPS are used to gauge the acceptability of proposed new practices by engaging with potential participants in the design of the intervention. This study will use TIP principles to explore and design culturally

appropriate cues to action or stimulus/triggers to action and motivational strategies to improve MMS adherence during pregnancy.

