In addition, attractive and informative packaging plays a crucial role in building a brand name (Keller KL, 2005). Studies have shown that recognized and reputable brand names are associated with increased consumer acceptance and adherence compared to generic drugs (Rafael GB et al, 2019; Faasse K, et al, 2013; Faasse K, et al, 2016). Thus, understanding women's and their partners' preferences regarding packaging design can help create a brand for antenatal MMS that is delivered through the national health system that promotes optimal use throughout pregnancy.

2. Study aims and objectives

This study aims to assess the relevance, acceptability, and utility of three interventions in supporting adherence to the MMS regimen of one tablet per day. The overall aims of the study are to:

1. Learn what pregnant women prefer regarding visual reminders and motivational messages to help them remember to take their MMS.
2. Identify challenges and supports that affect whether women can take their MMS daily throughout their pregnancy.
3. Work with end users (pregnant women) to design motivational messages and visual reminders that are culturally appropriate and relevant for the local community. These will be designed to help women consistently take one MMS tablet each day for the entire 180 days of their pregnancy.
4. To collect feedback from pregnant women and their partners regarding the packaging design for antenatal MMS delivered through the national health system. This feedback will be used to help finalize the MMS packaging design, including the color scheme, logo, brand name, and packaging features.

3. Study design

This is a longitudinal mixed-method study that uses a cross-over TIPS design. All enrolled pregnant women will be asked to take MMS for the duration of their pregnancy and will experience all three interventions in a specific order. In this way, everyone gets to experience each approach. The women will receive exposure to each intervention for 3-4 weeks. On approximately the fourth week, eighth week, and twelfth week of the study, the pregnant women will be asked to participate in a focus group discussion (FGD) with other women in the province who also received the same intervention the previous weeks. This process will be iterated in the same way for Intervention A, Intervention B, and Intervention C.

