- Paper notes will be kept safe in a locked cabinet, accessible only to the lead researchers (Principal Investigator and Co-Principal Investigator).

- Digital recordings will be password-protected and only authorized personnel can access them.

10. Data analysis plan

10a. Qualitative data analysis

Transcription and translation. All FGDs and the participatory workshops will be digitally recorded using ipads. Additionally, notetakers will be present to provide contextual notes and ensure accurate documentation of different speakers. The audio recordings from the FGDs and participatory workshops will be transcribed verbatim in English. Translation will be done simultaneously during transcription for interviews conducted in local languages. Transcribers will listen to the audio recordings in Khmer and translate and transcribe the interviews into English. The transcripts will be checked for quality by comparing them with the recorded audio and the notes taken by the notetakers.

After transcription is completed, a team of transcribers and coders will clean all FGD data. This cleaning process will involve tidying up partial sentences or words and writing out any abbreviations or acronyms. Any typos or abbreviations used in transcribing will be corrected directly in the text. All final transcripts will be reviewed for completeness and clarity before the analysis.

Data coding. The qualitative analysis team will read all typed transcripts and use a deductive-inductive approach for thematic content analysis. Initially, coding schemes will be developed based on the research questions and published literature for each intervention type (e.g. Intervention A, B, C) before data collection. These coding schemes will be refined and finalized after the lead researchers review a small set of transcripts and another small set by the assigned coders for accuracy and comprehensiveness. The coding schemes will then be shared and discussed with the rest of the research team before the assigned coders independently code the remaining transcripts. QSR NVivo software will be used to facilitate the coding and analysis of the data.

Data analysis. The qualitative analysis team will observe general patterns in the code summaries, focusing on context, descriptions, language, and narratives from the respondents' viewpoints. The analysis will include narratives and excerpts from focus group discussions to illustrate common themes, opinions, and viewpoints.

10b. Tablet counts

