From pill count data, descriptive analysis will be performed to measure daily adherence to MMS. During each focus group discussion, we will count the MMS tablets for each participant and calculate the eligible period for consumption from the 1st ANC date (pill received date) to the date of the focus group discussion. The mean number of tablets consumed will be calculated based on the eligibility of the consumption period. Adherence will be measured after the completion of each intervention, and differences in the mean will be measured. However, due to a very low sample size, no statistical test will be applied.

10c. Acceptability data

At the first focus group discussion, data collectors will ask pregnant women a quantitative acceptability questionnaire about MMS. A descriptive analysis will be conducted to determine the level of agreement (%) with each statement. However, due to a very low sample size, no statistical test will be applied.

11. Data custody, security, and protection of subject confidentiality

All data gathered during the study will be connected to identifiers and treated with the utmost confidentiality throughout and beyond the study period. Only the study's PIs and Co-PIs will have access to the data linked to the identifiers. The results of any analyses, presentations, or papers will be presented in aggregate to prevent individual disclosure. The survey will collect names of pregnant women only to ensure the accountability of the study team and to avoid duplication in the data collection/interviewing process. This information will be replaced with anonymous ID numbers for analysis, and the original data will be disposed of. Only members of the study team will be given access to the data.

Any paper notes collected during interviews will be kept in a locker until the final analysis is done. Once the analysis is done, all paper forms will be cut into pieces using a paper shredder machine. The data entry web-based platform will be password protected, and only a designated person can enter data. The data focal person will only have access to download and clean.

12. Risks and Benefits

Overall, the potential benefits of this study outweigh the minimal risks.

Benefits:

- Improved micronutrient status and improved birth outcomes: MMS is a proven effective intervention that improves maternal micronutrient status as well as improves birth outcomes, specifically reduces low birth weight, small for gestational weight, and pre-term births.

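### Focus-group themes (10a) and tablet counts (10b) are analysed apart, so the planned analysis does not check which voiced challenges or supports go with lower measured intake

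*Combined protocol and SAP*

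**What the plan says.** Aim 2 in section 2 reads: "Identify challenges and supports that affect whether women can take their MMS daily throughout their pregnancy".

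The analysis bearing on that aim is in two parts.

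- **Themes (10a).** Before data collection, "coding schemes will be developed based on the research questions and published literature for each intervention type". The coded material is then summarised: "The qualitative analysis team will observe general patterns in the code summaries, focusing on context, descriptions, language". The stated output is: "The analysis will include narratives and excerpts from focus group discussions to illustrate common themes, opinions, and viewpoints". Adherence level is not named as a way of dividing the material. Notetakers attend, among other things, to "ensure accurate documentation of different speakers".
- **Tablet counts (10b).** At each focus group "we will count the MMS tablets for each participant and calculate the eligible period for consumption", running from the date the tablets were received. The summary is: "The mean number of tablets consumed will be calculated based on the eligibility of the consumption period". Means are compared between interventions, and no test is planned because the sample is small.

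Section 7b assigns one set of woman-level data to the barrier and enabler analysis: the enrollment variables, such as age, BMI, haemoglobin, parity and gestational age. Tablet counts are not among them.

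The background describes interviews after an earlier Cambodian trial with "high adherers (>80%), low adherers (<80%), and those who did not complete the trial", and reports some barriers as belonging to low adherence and some facilitators as coming from high adherers.

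**The concern.** The tablet count is the study's only measure of intake, and the tool table in section 8 says its form is meant to assess the individual participant's adherence. In the analysis it becomes a group mean, and the themes become a general pattern per intervention. A challenge voiced by women who take nearly every tablet then looks the same as one voiced by women who miss many.

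If most attenders adhere well, the common themes will mainly describe adherers. The barriers of the few who miss tablets, whom the interventions are meant to help, may be diluted. The two strands of a study described as mixed-method would not inform each other.

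Timing matters too. Section 9 stores the count forms separately. Section 11 replaces names by ID numbers, disposes of the original data, and shreds paper forms after analysis. Unless speaker IDs are in the notes and transcripts from the start, the link may be hard to rebuild.

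**Working it through.** **1. The plan's own sample figure.** Section 5 gives 12-15 women in each of four provinces: 4 x 12 = 48 and 4 x 15 = 60, which reproduces the stated 48-60. With the stated 20% no-show, attendance per group is 12 x 0.8 = 9.6 to 15 x 0.8 = 12, so the target of 8-10 is met. No figure in the documents concerns the link between counts and themes, so that part of the check is textual.

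**2. Where the two strands could meet.**

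| Section | Themes | Tablet counts |
|---|---|---|
| 7b | enrollment data enter the barrier analysis | not mentioned |
| 7d, 7f | discussion at the focus group | count at the end of the same focus group |
| 9 | recordings and notes in one folder | paper forms stored separately |
| 10a | coded by intervention, general patterns | not mentioned |
| 10b | not mentioned | means and differences in means |
| 11 | ID numbers used for analysis, aggregate reporting | same |

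No section sets an adherence cut-off, divides themes by intake, or describes combining the strands.

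**3. How many low adherers a linked display would hold.** The documents give no adherence figure, so a 10-30% share below 80% is assumed.

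- Per focus group of 8-10: 8 x 0.10 = 0.8 to 10 x 0.30 = 3.
- Per round over four provinces: 4 x 0.8 = 3.2 to 4 x 3 = 12, or about 3-12 women.
- With the 20% no-show rate applied instead to 48-60 enrolled, 38 to 48 women attend (48 x 0.8 = 38.4, rounded down; 60 x 0.8 = 48). The same shares give 4-11 low adherers among 38 and 5-14 among 48.

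**4. What such numbers can support.** Suppose a theme is voiced by half of each group. The 95% half-width for the difference is 1.96 x sqrt(0.25/n_low + 0.25/n_high).

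- 4 versus 34: 1.96 x sqrt(0.0625 + 0.0074) = 0.52.
- 14 versus 34: 1.96 x sqrt(0.0179 + 0.0074) = 0.31.

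These are rough, because statements within a group are not independent. They show that the comparison can only be descriptive.

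**5. Which adherence to attach.** The eligible period in 10b always starts at tablet receipt, so it is cumulative. As an illustration, assume tablets received at the start of week 1 and groups held at the end of weeks 4, 8 and 12 (days 28, 56 and 84). A woman who takes every tablet in the first two rounds and half in the third has 14/28 = 50% in round 3, but (28 + 28 + 14)/84 = 83% cumulatively. On the 10b period she would be classed at or above 80% when discussing the intervention under which she missed half her tablets. A round-specific value needs the difference between successive counts.

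**The case against.** **Aim 2 does not mention tablets.** A reader might infer that aim 2 requires an association with missed tablets. Its text does not. It asks for challenges and supports, and thematic analysis of women's own accounts identifies those. This stands: the linked display would help answer the aim, but the aim does not literally demand it.

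**The data are adequate.** A reader might also infer that the study is unable to relate barriers to intake. That goes too far. Counts are taken for each woman, speakers are documented, and ID numbers are used. The gap is in the planned analysis.

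**Woman-level data already enter.** Coding is by intervention, and 7b brings enrollment data into the barrier analysis. Both are true, but neither covers intake.

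**The earlier split came from individual interviews.** In a focus group, statements depend on the other speakers, and silence does not mean that a barrier is absent. This stands as a limit on interpretation. Inductive coding and a moderator who gives everyone a chance to speak also allow minority barriers to surface, but do not show whether they go with low intake.

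**Section 5 reports little variation between women.** That statement concerns acceptability and the perceived benefits of strategies. The background reports different themes for high and low adherers.

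**The cut in the background.** Read literally, it leaves a woman at exactly 80% in neither group. A reader might count that as an error here. It describes another study's interviewees, and the present plan sets no cut-off.

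**Small cells.** With 1-3 low adherers per provincial group, a display by province could conflict with the aggregate reporting in section 11. This stands, and is why the display should be pooled.

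**Conclusion.** The point holds as a gap in the analysis plan. Followed as written, 10a and 10b leave themes and measured intake unconnected, although both are collected from the same women at the same session. A descriptive joint display is a better use of those data. The documents do not support a claim that aim 2 goes unanswered or that the data collection is deficient.

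The size is modest and rests on an assumed share of low adherers: about 3-12 women per round if 10-30% of attenders are below 80%. Women who miss a focus group give neither a count nor a statement there, so linkage does not reach them.

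**What to change.** **In 10a:** label speakers by study ID in notes and transcripts, and attach each woman's tablet-count adherence. Add a descriptive joint display of barriers and enablers by adherence level for each intervention, for example at least 80% versus below 80%, so that every woman with a count is classified. Pool it over the four provinces and apply no statistical test.

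**In 10b:** define round-specific adherence as the difference between successive counts divided by the days between them. Use the cumulative value from tablet receipt at round 1, or when the prior count is missing. Report the percentage of women at or above 80% beside the mean.

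**State as limits:** some utterances will be unattributed, low-adherer numbers will be small, silence in a group is not absence of a barrier, and non-attenders are not captured.

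**Cost:** plan wording and modest extra coding, with no new data collection. Labels must use IDs only, and the practice must begin with the first focus group.

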For the TIPS, the sample size of 48-60 women (around 12-15 women per province) is purposive but has been selected for two reasons. First, the sample size of 12-15 women per province allows enough women to participate in a FGD. Considering that an ideal number for FGD is 8-10 people if 20% of the participants are expected not to show, there would still be enough participants to conduct an FGD. Second, based on previous formative research with pregnant women in Kampong Thom, there was not much variation in the experiences of women regarding MMS acceptability and their perceptions of the benefits of various strategies to improve adherence. Thus, one FGD per province is believed to be sufficient to capture the range of perspectives on the different interventions and achieve saturation, or the point at which no new significant themes or insights emerge from the data.

For the participatory workshops to design the MMS product package, approximately 100 participants will be recruited across four provinces in Cambodia (25 participants per workshop, 4 workshops total). Participants will be pregnant women who have previously participated in the TIPS program and their husbands/partners. The sample size is a convenience sample and chosen for the following reasons. First, it is anticipated that with a focused group like pregnant women and their partners who have a shared experience with the TIPS program, 25 per province is likely enough to reach saturation. Second, the study must consider logistical manageability and group dynamics. With 25 participants, workshops can maintain a manageable size for group discussions and activities. This allows for active participation, ensures everyone has a chance to be heard, and facilitates effective interaction. Thirdly, smaller workshops require fewer facilitators, materials, and space, making them more cost-effective and easier to organize across four different provinces.

6. Participant recruitment and selection

The research team will aim to recruit 12-15 pregnant women attending their first ANC per province. Ideally, from 8-10 of these women will then join the FGD to discuss their experiences with that specific intervention (see Table 1).

Figure 1. TIPS sample size per province

Week	Interventions	Kampong Chhnang	Rattanakiri	Takeo	Kampot	Total
1-3	A	12-15	12-15	12-15	12-15	48-60
4	Focus Group Discussions					
5-7	B	Same women	Same women	Same women	Same women	
8	Focus Group Discussions					

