Selected healthcare providers (e.g. midwives, doctors) from the primary health center will attend an orientation and training on the objectives and design of the study, the benefits of IFA or MMS supplementation during pregnancy, and any expected risks with participation. Healthcare providers will be trained on the protocol for enrollment (e.g., inclusion and exclusion criteria), obtaining verbal consent, and recording registration data. A primary healthcare worker in the health center (receiving an incentive payment from the study) will invite pregnant women to participate, give an overview of the study, including any risks, and ensure they meet all inclusion criteria. Healthcare workers will obtain verbal informed consent, provide the MMS-180, and explain that the study team will contact the participants within 72 hours and visit them in their homes to obtain written informed consent. If the woman agrees, she will provide her contact number, which the healthcare worker will submit to the study team by the end of the day. The women will then receive MMS-180 and be counseled on its use. A member of the study team will reach out to the new participant ideally within 72 hours to confirm participation, informed consent, and that the woman received the supplements. Up to two weeks will be allowed from the time of verbal informed consent at the health center until written consent is obtained at the participant's home. A record of all women screened but not enrolled will be maintained. The enrollment form is included in Annex A and the informed consent form for TIPS is included in Annex B. The informed consent form for the participatory workshop is in Annex C.

7. Study procedures

In each of the four health centers, a designated healthcare provider will enroll up to 15 pregnant women with first ANC visit. All women will receive all three interventions (family support, wall calendars, social media posts and videos) sequentially over 12 weeks. Women will be exposed to each intervention for 3-4 weeks, followed by a FGD to share their experiences and feedback. This iterative process helps researchers improve the interventions for better MMS adherence during pregnancy.

7a. Participant allocation

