There is no allocation to any intervention group. Each enrolled woman receives all interventions in a specific sequence. Per province, in each health facility, the study team will purposively select pregnant women to ensure a diversity in sociodemographic characteristics. This helps ensure the interventions are appropriate for a broad range of women. After ensuring written informed consent, the eligible pregnant women will be asked to participate in taking MMS and arm experience all three interventions (A, B, and C) in a specific order. The sequence for each study arm and their exposure to the intervention is shown in Figure 2. This allows researchers to compare a participant's experience with each intervention.

7b. Enrollment data

Demographic and other enrollment data, such as gestational age at enrollment, maternal age, maternal BMI, maternal Hb, parity, as well as contact information and detailed directions to home of residence, will be collected from the health facility. This data will be included in the analysis for adherence, acceptability, and barriers and enablers.

7c. Intervention description

- **Intervention A (MMS + Family support):** 180 tablets of MMS and daily encouragement and help from family members. Family members will receive an orientation on supporting pregnant women and encouraged them to provide daily motivational reminders until she finished 180 pills
- **Intervention B (MMS + Visual reminders):** 180 tablets of MMS and wall calendars with health information and motivational messages will be provided.
- **Intervention C (MMS + Social media posts and videos):** 180 tablets of MMS and 2-3 times/weekly social media posts and videos educational and motivational messages from healthcare providers delivered through social media posts and videos. Messages will emphasize its benefits and offer encouragement.

Figure 2: Weeks 1-14, Testing of interventions across all study arms and participant FGDs

Intervention	Week 1-3	Week 4	Week 5-7	Week 8	Week 9-11	Week 12	Week 13-14
A	Intervention A	Focus Group Discussion A	Intervention B	Focus Group Discussion B	Intervention C	Focus Group Discussion C	Participatory Workshop
B	X	X					X
C			X	X	X	X	X

7d. Conduct of focus group discussions

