At each FGD, pregnant women will be asked to bring with them their MMS bottle. At the end of each FGD, the research team will conduct a tablet count. The research team will explain that they will quickly count the woman’s remaining MMS tablets by transferring the pills to a clean bag, counting them, and then returning them without touching them. After putting on fresh gloves, the trained researcher will open the medication bottle, pour the pills into a sealed bag, and place all pills flat with pills on one side. Using gloved hands, the researcher will count the pills, moving them one by one or grouping them by ten for easier counting. The count will be recorded twice. If the counts differ, they will repeat the process once more and record the final number. Finally, a small corner of the bag will be snipped, and the pills with the desiccant will be carefully poured back into the bottle before securing the lid. See Annex G for the tablet count sheet.

7g. Acceptability survey

During the FGD with pregnant women, all participants will be asked to fill out a survey to gather their opinions on various sensory aspects of the MMS. The survey will inquire about their preferences regarding the taste, smell, size, color, and ease of swallowing the pill. Participants will be asked to rate their opinions on a scale ranging from "strongly disagree" to "strongly agree," with options including "disagree," "neutral," and "agree." Each option will be represented by a corresponding mood emoji on the survey form. The survey is designed to be completed within 5 minutes and will be administered at the conclusion of the FGD. See Annex H for a copy of the acceptability survey form.

7h. Incentives for participants

Mobile data (KHR 15,000) will be provided for all women to see the social media posts and videos. In addition, a sarong, a towel, local fruits, or local nutritious food products (e.g. fish powder, dried fish) will be provided after each FGD and/or participatory workshop to respect participants’ time and valuable participation in the FGDs and/or participatory workshop. These items were selected as incentives as they are believed to be valuable enough to show appreciation to respondents for their time, but not so valuable that they will cause undue influence in study participation.

8. Data collection methods and tools

Tool	Purpose	Annex No.

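### Section 10b measures every tablet count from first ANC, so the week-8 and week-12 adherence figures are running averages and no adherence figure per intervention is defined

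*Combined protocol and SAP*

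**What the plan says.** Section 7f provides a count at every FGD: "At the end of each FGD, the research team will conduct a tablet count". Section 3 places the three FGDs: "On approximately the fourth week, eighth week, and twelfth week of the study, the pregnant women will be asked to participate".

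Section 10b gives the only rule for turning a count into adherence. The team will "calculate the eligible period for consumption from the 1st ANC date (pill received date) to the date of the focus group discussion", and mean tablets taken is worked out against that period. It continues: "Adherence will be measured after the completion of each intervention, and differences in the mean will be measured". No test is applied.

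Two other provisions bear on the rule:

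- **Schedule.** The tables headed "Figure 1. TIPS sample size per province" (section 6) and "Figure 2: Weeks 1-14, Testing of interventions across all study arms and participant FGDs" (section 7c) put A in weeks 1–3, B in weeks 5–7 and C in weeks 9–11, with FGDs in weeks 4, 8 and 12.
- **Tablet supply.** Section 6e has tablets handed over at the first antenatal (ANC) visit: "The women will then receive MMS-180 and be counseled on its use". Written consent comes later: "Up to two weeks will be allowed from the time of verbal informed consent at the health center until written consent is obtained".

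Neither 7f nor 10b restarts the period at the previous FGD or at the start of an intervention, and neither subtracts an earlier count.

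**The concern.** The comparison in 10b is between interventions, but the only window it defines is cumulative. Under that window, adherence during A is carried into the figure reported after B, and adherence during A and B into the figure reported after C. Any days between tablet receipt and the start of A enter all three.

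Section 3 expects the design to show which intervention performs best, and the tablet count is the study's only objective adherence measure. A reader who takes the three means as figures for A, B and C could see real differences shrunk, hidden or reversed. The start dates of A, B and C do not enter the calculation either, so the report could not show how much of each window belongs to the intervention it is labelled with.

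**Working it through.** The plan states no adherence figure to reproduce. The weights below follow from the written window and the schedule. The adherence values are assumed, for illustration only.

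**Inputs.** One tablet per day (section 2). Fixed order A, B, C in the same women (section 7a). Periods of 28 days, from FGDs in weeks 4, 8 and 12. Assumed true adherence a = 60%, b = 90%, c = 80%.

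**1. Rule as written, no days before A, count on the day the next intervention starts.**

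- Week 4: a = 60%
- Week 8: (a + b)/2 = (60 + 90)/2 = 75.0%
- Week 12: (a + b + c)/3 = 230/3 = 76.7%

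The reported B−A is (b − a)/2, so it is halved but keeps its sign. The reported C−B is (2c − a − b)/6 = (160 − 150)/6 = +1.7 points; the true value is −10. The sign of C−B therefore depends on whether C beats the average of A and B, not on whether it beats B. Other assumed patterns: 70/80/90% is reported as 70/75/80% (order kept, C−A halved from 20 to 10 points), and 90/70/80% as 90/80/80% (a 10-point difference hidden).

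**2. Days before A.** With r days at A's rate, A makes up 28/(28 + r) of its own window, B 28/(56 + r) and C 28/(84 + r). Section 6e names 72 hours (ideal contact) and two weeks (limit for written consent). The plan sets no limit on the gap to the start of A itself.

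| r (days) | A's share | B's share | C's share | Reported for 60/90/80% |
|---|---|---|---|---|
| 0 | 100% | 50% | 33% | 60 / 75.0 / 76.7% |
| 3 | 90% | 47% | 32% | 60 / 74.2 / 76.1% |
| 14 | 67% | 40% | 29% | 60 / 72.0 / 74.3% |

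**3. FGD-week gap.** The count falls in week 4 or 8 and the next intervention starts in week 5 or 9, so up to about 7 days can pass between them. Let s be that gap, with the previous rate kept during it.

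- Cumulative: B = (28a + (28 − s)b)/(56 − s); C = (28a + 28b + (28 − s)c)/(84 − s)
- Count to count: B = (s·a + (28 − s)b)/28; C = (s·b + (28 − s)c)/28

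| s (days) | Cumulative A/B/C | C−B | Count-to-count A/B/C | C−B |
|---|---|---|---|---|
| 0 | 60 / 75.0 / 76.7% | +1.7 | 60 / 90 / 80% | −10 |
| 3.5 | 60 / 74.0 / 76.5% | +2.5 | 60 / 86.3 / 81.3% | −5 |
| 7 | 60 / 72.9 / 76.4% | +3.5 | 60 / 82.5 / 82.5% | 0 |

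Over s = 0 to 7, the share of each intervention in its own figure is 43–50% (B) and 27–33% (C) under the cumulative rule, and 75–100% for both when counting from one FGD to the next.

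**4. Subtracting group means when attendance changes.** Suppose 8 of 10 women take 90% and 2 take 40% throughout, and those 2 miss week 8. The week-4 mean is (8 × 25.2 + 2 × 11.2)/10 = 22.4 tablets. The week-8 mean in the remaining 8 is 50.4. The difference, 28.0 tablets over 28 days, implies 100% adherence, although nobody exceeds 90%.

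**The case against.** The strongest reply is that 10b speaks of the mean number of tablets and of differencing means. If these are cumulative tablet counts, the 60/90/80% example gives 16.8, 42.0 and 64.4 tablets. Successive differences are 25.2 and 22.4 per 28 days, exactly 90% and 80%. That reading is possible, but the text does not state it. It needs the same women at each count (step 4), while section 5 allows for 20% not attending, and it leaves the FGD-week gap in place.

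Other points stand in part:

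- The reversal of C−B needs a particular pattern; a steadily rising one keeps its order.
- The analysis is descriptive, the four numbered aims are mainly about preferences, barriers and design, and the FGDs ask women directly how well each intervention helped. This limits the consequence.
- The order is fixed and section 7c has family reminders continue until the tablets are used up. Even a correct interval would therefore not isolate B or C.
- The tablet count sheet (Annex G in section 7f) is not in the text reviewed and may already record dates or intervals.

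None of this supplies a definition of adherence per period in the analysis section.

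**Conclusion.** The concern holds and should be fixed before the counts are analysed. As written, one start date serves all three counts, so the figures reported after B and after C pool earlier interventions. With 28-day periods and no lead-in, B has weight one half and C one third in its own figure, and any lead-in or FGD-week gap lowers these weights. B−A is diluted; comparisons involving C can be misstated in either direction.

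The weights rest on the schedule and on 28-day periods. The size of the distortion depends on adherence values that are not known. No error rate or sample size is affected. Counting from one FGD to the next removes most of the distortion, but not all of it while a gap remains between the count and the next intervention.

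**What to change.** Reword 10b along these lines:

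- **Period adherence** = (tablets remaining at the previous count + tablets dispensed since − tablets remaining now) / days between the two counts, in women with both counts, with their number reported. For A, start from the supply given at first ANC. The dispensing term is needed because sections 3 and 7c list 180 tablets under each intervention while 6e describes one supply at enrollment; those sections should be reconciled.
- **Start dates.** Record when A, B and C start. Report how many days of each interval precede the intervention: up to about 7 of 28 for B and C, and for A the gap from tablet receipt.
- **Missed FGDs.** Do not assign an interval that spans a missed FGD to one intervention. In the example, weeks 4–12 give (90 + 80)/2 = 85%, which is neither B nor C.
- **Comparison.** Compare periods only in the same women, and describe the results as successive periods, not as isolated effects.
- **Overall adherence.** Keep the cumulative figure from first ANC under that name.

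No new count is needed. Check whether Annex G already holds count dates and tablets dispensed. Keep each woman's counts and dates linked in the electronic data, because section 11 has paper forms shredded after analysis.

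The cost is fewer usable women. If a proportion p attends each FGD, two counts exist in 2p − 1 to p of women (p² if absences are independent), and three counts, needed for any same-women comparison with C, in max(0, 3p − 2) to p (p³ if independent). Out of 48–60 women:

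| Attendance | Two counts | Three counts |
|---|---|---|
| 80% (section 5) | 60–80%; 64% if independent, 31–38 women | 40–80%; 51% if independent, 25–31 women |
| 8–10 of 12–15, about 67% (section 6) | 33–67%; 44% if independent, 21–27 women | 0–67%; 30% if independent, 14–18 women |

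Women who attend all three FGDs may also differ in adherence from the rest, so report the all-women period figures beside the same-women comparison.
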